5.1.5 Safety Risks Associated with Fulvestrant

In a Phase III randomized, double-blind, clinical trial that compared a 500-mg dose of fulvestrant with a 250-mg dose in 736 postmenopausal women with advanced breast cancer who had disease recurrence on or after adjuvant endocrine therapy or progression following endocrine therapy for advanced disease, the most frequently reported adverse events in the 500-mg group were injection-site pain (11.6% of patients),

nausea (9.7%), and bone pain (9.4%); in the 250-mg group, they were nausea (13.6%), back pain (10.7%), and injection-site pain (9.1%). In the pooled safety population from clinical trials comparing fulvestrant 500 mg to 250 mg, postbaseline increase of Grade ≥ 1 AST, ALT, or ALP were observed in $> 15\%$ of patients, with Grade 3–4 increases in 1%–2% of patients. Because fulvestrant is administered intramuscularly, it should be used with caution in patients with bleeding diatheses, thrombocytopenia, or anticoagulant use.

For more details regarding the safety profile of fulvestrant, please refer to the fulvestrant (e.g., FASLODEX[®]) Package Insert or SmPC.

5.1.5.1 General Guidance for Fulvestrant Dose Modifications

The fulvestrant dose level cannot be modified. In general, the investigator may consider continuing fulvestrant if the observed adverse event is not thought to be fulvestrant related.

If a scheduled dose coincides with a holiday or inclement weather or other conditions that preclude dosing, dosing should commence on the nearest following date. Subsequent dosing should continue on the original 28-day schedule.

5.2 SAFETY PARAMETERS AND DEFINITIONS

Safety assessments will consist of monitoring and recording adverse events, including serious adverse events and non-serious adverse events of special interest, performing protocol-specified safety laboratory assessments, measuring protocol-specified vital signs, and conducting other protocol-specified tests that are deemed critical to the safety evaluation of the study.

Certain types of events require immediate reporting to the Sponsor, as outlined in Section 5.4.

5.2.1 Adverse Events

According to the ICH guidelines for GCP, an adverse event is any untoward medical occurrence in a clinical investigation subject administered a pharmaceutical product, regardless of causal attribution. An adverse event can therefore be any of the following:

- Any unfavorable and unintended sign (including an abnormal laboratory finding), symptom, or disease temporally associated with the use of a medicinal product, whether or not considered related to the medicinal product
- Any new disease or exacerbation of an existing disease (a worsening in the character, frequency, or severity of a known condition), except as described in Section 5.3.5.9
- Recurrence of an intermittent medical condition (e.g., headache) not present at baseline

- Any deterioration in a laboratory value or other clinical test (e.g., ECG, X-ray) that is associated with symptoms or leads to a change in study treatment or concomitant treatment or discontinuation from study drug
- Adverse events that are related to a protocol-mandated intervention, including those that occur prior to assignment of study treatment (e.g., screening invasive procedures such as biopsies)

5.2.2 Serious Adverse Events (Immediately Reportable to the Sponsor)

A serious adverse event is any adverse event that meets any of the following criteria:

- Is fatal (i.e., the adverse event actually causes or leads to death)
- Is life-threatening (i.e., the adverse event, in the view of the investigator, places the patient at immediate risk of death)

This does not include any adverse event that had it occurred in a more severe form or was allowed to continue might have caused death.

- Requires or prolongs inpatient hospitalization (see Section [5.3.5.10](#))
- Results in persistent or significant disability/incapacity (i.e., the adverse event results in substantial disruption of the patient's ability to conduct normal life functions)
- Is a congenital anomaly/birth defect in a neonate/infant born to a mother exposed to study drug
- Is a significant medical event in the investigator's judgment (e.g., may jeopardize the patient or may require medical/surgical intervention to prevent one of the outcomes listed above)

The terms "severe" and "serious" are not synonymous. Severity refers to the intensity of an adverse event (e.g., rated as mild, moderate, or severe, or according to NCI CTCAE criteria; see Section [5.3.3](#)); the event itself may be of relatively minor medical significance (such as severe headache without any further findings).

Severity and seriousness need to be independently assessed for each adverse event recorded on the eCRF.

Serious adverse events are required to be reported by the investigator to the Sponsor immediately (i.e., no more than 24 hours after learning of the event; see Section [5.4.2](#) for reporting instructions).

5.2.3 Non-Serious Adverse Events of Special Interest (Immediately Reportable to the Sponsor)

Non-serious adverse events of special interest are required to be reported by the investigator to the Sponsor immediately (i.e., no more than 24 hours after learning of the event; see Section 5.4.2 for reporting instructions). Adverse events of special interest for this study include the following:

- Cases of potential drug-induced liver injury that include an elevated ALT or AST in combination with either an elevated bilirubin or clinical jaundice, as defined by Hy's law (see Section 5.3.5.6)
- Suspected transmission of an infectious agent by the study drug, as defined below
Any organism, virus, or infectious particle (e.g., prion protein transmitting transmissible spongiform encephalopathy), pathogenic or non-pathogenic, is considered an infectious agent. A transmission of an infectious agent may be suspected from clinical symptoms or laboratory findings that indicate an infection in a patient exposed to a medicinal product. This term applies only when a contamination of the study drug is suspected.
- Grade ≥ 2 diarrhea or vomiting
- Grade ≥ 3 nausea
- Grade ≥ 2 vaginal or uterine hemorrhage (Grade 2 is defined as moderate bleeding; medical intervention indicated)
- Grade ≥ 2 thromboembolic event (*including* pulmonary embolism)
- *Grade ≥ 3 elevation of ALT or AST*

5.3 METHODS AND TIMING FOR CAPTURING AND ASSESSING SAFETY PARAMETERS

The investigator is responsible for ensuring that all adverse events (see Section 5.2.1 for definition) are recorded on the Adverse Event eCRF and reported to the Sponsor in accordance with instructions provided in this section and in Section 5.4 to Section 5.6.

For each adverse event recorded on the Adverse Event eCRF, the investigator will make an assessment of seriousness (see Section 5.2.2 for seriousness criteria), severity (see Section 5.3.3), and causality (see Section 5.3.4).

5.3.1 Adverse Event Reporting Period

Investigators will seek information on adverse events at each patient contact. All adverse events, whether reported by the patient or noted by study personnel, will be recorded in the patient's medical record and on the Adverse Event eCRF.

After informed consent has been obtained **but prior to initiation of study drug**, only serious adverse events caused by a protocol-mandated intervention (e.g., invasive procedures such as biopsies, discontinuation of medications) should be reported (see Section 5.4.2 for instructions for reporting serious adverse events).

After initiation of study drug, all adverse events will be reported until 28 days after the last dose of study drug. After this period, the investigator should report any serious adverse events that are believed to be related to prior study drug treatment (see Section 5.6).

5.3.2 Eliciting Adverse Event Information

A consistent methodology of non-directive questioning should be adopted for eliciting adverse event information at all patient-evaluation timepoints. Examples of non-directive questions include the following:

"How have you felt since your last clinic visit?"

"Have you had any new or changed health problems since you were last here?"

5.3.3 Assessment of Severity of Adverse Events

The adverse event severity grading scale for the NCI CTCAE (v4.0) will be used for assessing adverse event severity. Table 2 will be used for assessing severity for adverse events that are not specifically listed in the NCI CTCAE.

Table 2 Adverse Event Severity Grading Scale for Events Not Specifically Listed in NCI CTCAE

Grade	Severity
1	Mild; asymptomatic or mild symptoms; clinical or diagnostic observations only; or intervention not indicated
2	Moderate; minimal, local, or non-invasive intervention indicated; or limiting age-appropriate instrumental activities of daily living ^a
3	Severe or medically significant, but not immediately life-threatening; hospitalization or prolongation of hospitalization indicated; disabling; or limiting self-care activities of daily living ^{b,c}
4	Life-threatening consequences or urgent intervention indicated ^d
5	Death related to adverse event ^d

NCI CTCAE = National Cancer Institute Common Terminology Criteria for Adverse Events.

Note: Based on the most recent version of NCI CTCAE (v4.0), which can be found at: http://ctep.cancer.gov/protocolDevelopment/electronic_applications/ctc.htm

^a Instrumental activities of daily living refer to preparing meals, shopping for groceries or clothes, using the telephone, managing money, etc.

^b Examples of self-care activities of daily living include bathing, dressing and undressing, feeding oneself, using the toilet, and taking medications, as performed by patients who are not bedridden.

^c If an event is assessed as a "significant medical event," it must be reported as a serious adverse event (see Section 5.4.2 for reporting instructions), per the definition of serious adverse event in Section 5.2.2.

^d Grade 4 and 5 events must be reported as serious adverse events (see Section 5.4.2 for reporting instructions), per the definition of serious adverse event in Section 5.2.2.

5.3.4 Assessment of Causality of Adverse Events

Investigators should use their knowledge of the patient, the circumstances surrounding the event, and an evaluation of any potential alternative causes to determine whether or not an adverse event is considered to be related to the study drug, indicating "yes" or "no" accordingly. The following guidance should be taken into consideration (see also [Table 3](#)):

- Temporal relationship of event onset to the initiation of study drug
- Course of the event, considering especially the effects of dose reduction, discontinuation of study drug, or reintroduction of study drug (as applicable)
- Known association of the event with the study drug or with similar treatments
- Known association of the event with the disease under study
- Presence of risk factors in the patient or use of concomitant medications known to increase the occurrence of the event
- Presence of non-treatment-related factors that are known to be associated with the occurrence of the event

Table 3 Causal Attribution Guidance

Is the adverse event suspected to be caused by the study drug on the basis of facts, evidence, science-based rationales, and clinical judgment?	
YES	There is a plausible temporal relationship between the onset of the adverse event and administration of the study drug, and the adverse event cannot be readily explained by the patient's clinical state, intercurrent illness, or concomitant therapies; and/or the adverse event follows a known pattern of response to the study drug; and/or the adverse event abates or resolves upon discontinuation of the study drug or dose reduction and, if applicable, reappears upon re-challenge.
NO	An adverse event will be considered related, unless it fulfills the criteria specified below. Evidence exists that the adverse event has an etiology other than the study drug (e.g., preexisting medical condition, underlying disease, intercurrent illness, or concomitant medication); and/or the adverse event has no plausible temporal relationship to administration of the study drug (e.g., cancer diagnosed 2 days after first dose of study drug).

For patients receiving combination therapy, causality will be assessed individually for each protocol-mandated therapy.

5.3.5 Procedures for Recording Adverse Events

Investigators should use correct medical terminology/concepts when recording adverse events on the Adverse Event eCRF. Avoid colloquialisms and abbreviations.

Only one adverse event term should be recorded in the event field on the Adverse Event eCRF.

5.3.5.1 Diagnosis versus Signs and Symptoms

A diagnosis (if known) should be recorded on the Adverse Event eCRF rather than individual signs and symptoms (e.g., record only liver failure or hepatitis rather than jaundice, asterixis, and elevated transaminases). However, if a constellation of signs and/or symptoms cannot be medically characterized as a single diagnosis or syndrome at the time of reporting, each individual event should be recorded on the Adverse Event eCRF. If a diagnosis is subsequently established, all previously reported adverse events based on signs and symptoms should be nullified and replaced by one adverse event report based on the single diagnosis, with a starting date that corresponds to the starting date of the first symptom of the eventual diagnosis.

5.3.5.2 Adverse Events That Are Secondary to Other Events

In general, adverse events that are secondary to other events (e.g., cascade events or clinical sequelae) should be identified by their primary cause, with the exception of severe or serious secondary events. A medically significant secondary adverse event that is separated in time from the initiating event should be recorded as an independent event on the Adverse Event eCRF. For example:

- If vomiting results in mild dehydration with no additional treatment in a healthy adult, only vomiting should be reported on the eCRF.
- If vomiting results in severe dehydration, both events should be reported separately on the eCRF.
- If a severe GI hemorrhage leads to renal failure, both events should be reported separately on the eCRF.
- If dizziness leads to a fall and consequent fracture, all three events should be reported separately on the eCRF.
- If neutropenia is accompanied by an infection, both events should be reported separately on the eCRF.

All adverse events should be recorded separately on the Adverse Event eCRF if it is unclear as to whether the events are associated.

5.3.5.3 Persistent or Recurrent Adverse Events

A persistent adverse event is one that extends continuously, without resolution, between patient evaluation timepoints. Such events should only be recorded once on the Adverse Event eCRF. The initial severity (intensity or grade) of the event will be recorded at the time the event is first reported. If a persistent adverse event becomes more severe, the most extreme severity should also be recorded on the Adverse Event eCRF. Details regarding any increases or decreases in severity will be captured on the Adverse Event Grade Changes eCRF. If the event becomes serious, it should be reported to the Sponsor immediately (i.e., no more than 24 hours after learning that the event became serious; see Section 5.4.2 for reporting instructions). The Adverse Event eCRF should be updated by changing the event from "non-serious" to "serious,"

providing the date that the event became serious, and completing all data fields related to serious adverse events.

A recurrent adverse event is one that resolves between patient evaluation timepoints and subsequently recurs. Each recurrence of an adverse event should be recorded as a separate event on the Adverse Event eCRF.

5.3.5.4 Abnormal Laboratory Values

Not every laboratory abnormality qualifies as an adverse event. A laboratory test result must be reported as an adverse event if it meets any of the following criteria:

- Is accompanied by clinical symptoms
- Results in a change in study treatment (e.g., dosage modification, treatment interruption, or treatment discontinuation)
- Results in a medical intervention (e.g., potassium supplementation for hypokalemia) or a change in concomitant therapy
- Is clinically significant in the investigator's judgment

Note: For oncology trials, certain abnormal values may not qualify as adverse events.

It is the investigator's responsibility to review all laboratory findings. Medical and scientific judgment should be exercised in deciding whether an isolated laboratory abnormality should be classified as an adverse event.

If a clinically significant laboratory abnormality is a sign of a disease or syndrome (e.g., ALP and bilirubin $5 \times$ ULN associated with cholestasis), only the diagnosis (i.e., cholestasis) should be recorded on the Adverse Event eCRF.

If a clinically significant laboratory abnormality is not a sign of a disease or syndrome, the abnormality itself should be recorded on the Adverse Event eCRF, along with a descriptor indicating if the test result is above or below the normal range (e.g., "elevated potassium," as opposed to "abnormal potassium"). If the laboratory abnormality can be characterized by a precise clinical term per standard definitions, the clinical term should be recorded as the adverse event. For example, an elevated serum potassium level of 7.0 mEq/L should be recorded as "hyperkalemia."

Observations of the same clinically significant laboratory abnormality from visit to visit should only be recorded once on the Adverse Event eCRF (see Section 5.3.5.4 for details on recording persistent adverse events).

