5.1.4.3 Renal Dysfunction

Nonclinical toxicity studies have demonstrated minimal-to-mild microscopic findings in animal kidneys (kidney tubular degeneration, dilation, mineralization), which were completely reversible upon cessation of study drug. *As of 9 September 2016, the adverse event term of acute kidney injury was reported in 2 (1.3%) patients across all phases of Study GO29642 (combined n=148), neither case was considered related to GDC-0810.*

Renal function tests will be closely monitored, and GDC-0810 treatment should be held for Grade ≥ 2 creatinine elevation. GDC-0810 may be resumed if creatinine improves to normal or baseline value, whichever is higher.

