6.5 SAFETY ANALYSES

The safety analyses will include all randomized patients who received at least one dose of study drug, with patients grouped according to the treatment actually received. Safety will be assessed through summaries of adverse events, changes in laboratory test results, changes in vital signs, and GDC-0810 exposure.

Drug exposure will be summarized, which includes duration of treatment, number and intensity of dose.

Verbatim descriptions of adverse events will be mapped to thesaurus terms. Adverse-event data will be listed by study site, treatment arm, patient number, and study day. All adverse events occurring during or after the first dose of study treatment will be summarized by thesaurus term, appropriate thesaurus levels, treatment arm, and NCI CTCAE v4.0 grade. In addition, serious adverse events, severe adverse events (Grade ≥ 3), adverse events of special interest, and adverse events leading to study drug discontinuation or interruption will be listed separately and summarized accordingly. Multiple occurrences of the same event will be counted once at the maximum severity.

Deaths reported during the study will be summarized by treatment arm, including reasons leading to death.

Relevant laboratory and vital sign (heart rate, blood pressure, and temperature) data will be displayed by time, with NCI CTCAE Grades 3 and 4 values identified, where appropriate. Additionally, all laboratory data will be summarized by NCI CTCAE v4.0 grade.

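### An isolated Grade 2 or higher creatinine rise is a mandatory adverse event on GDC-0810 but rests on open-label investigator judgment on fulvestrant, so creatinine adverse event counts are not ascertained equally by arm

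*Combined protocol and SAP*

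**What the plan says.** **Reporting rule.** Section 5.3.5.4 opens its list with "A laboratory test result must be reported as an adverse event if it meets any of the following criteria". There are four alternative criteria. The first is "Is accompanied by clinical symptoms". The second is that the result "Results in a change in study treatment (e.g., dosage modification, treatment interruption, or treatment discontinuation". The third is a medical intervention or a change in concomitant therapy, and the fourth is the investigator's view that the result is clinically significant. The adverse event definition in Section 5.2.1 also covers a laboratory deterioration that "leads to a change in study treatment or concomitant treatment or discontinuation from study drug".

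**Arm A.** Section 5.1.4.3 lists renal dysfunction as a potential risk and states that "GDC-0810 treatment should be held for Grade ≥ 2 creatinine elevation". Section 5.1.4.6 repeats the hold.

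**Arm B.** Section 5.1.5.1 states that "The fulvestrant dose level cannot be modified" and lets the investigator consider continuing if an event is not thought to be fulvestrant related. It gives no creatinine or other laboratory threshold. Section 4.3.2.2 refers to that section for guidance on interruption and discontinuation, so stopping or delaying fulvestrant is contemplated.

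**Analysis.** The safety objective in Section 2.2 compares the two drugs on the kind, frequency and severity of adverse events. Section 6.5 summarises adverse events by arm, and separately those leading to discontinuation or interruption. It also states: "Additionally, all laboratory data will be summarized by NCI CTCAE v4.0 grade".

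**The concern.** One of the mandatory triggers depends on what is done to study treatment, and the protocol directs a treatment action for creatinine in one arm only. Two patients with the same asymptomatic value can then be counted differently because of their assignment. The part of the rule left to judgment falls mainly on the control arm, and Section 4.2 confirms that investigators know the assignment. Section 3.3.4 itself acknowledges the risk of bias from the open-label design.

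The plan avoids this problem for another analyte. Section 5.2.3 lists "Grade ≥ 3 elevation of ALT or AST" as an adverse event of special interest for the study, with no condition on treatment change. Creatinine has no equivalent entry, although renal dysfunction is a named potential risk and Section 5.1.4.3 describes the earlier clinical experience through an adverse event term.

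At stake is the reading of the renal lines in the adverse event tables, including the table of events leading to interruption. The adverse event and laboratory tables could give different pictures of the same risk, and Section 6.5 does not say which one carries the comparison.

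**Working it through.** The plan gives no figure on this point to reproduce. The check sets the rules side by side and then illustrates the size.

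**Step 1. Follow one isolated, asymptomatic Grade 2 creatinine rise that needs no medical intervention and no concomitant-therapy change.**

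| Criterion in 5.3.5.4 | Arm A, managed as written | Arm B |
|---|---|---|
| Symptoms | Not met | Not met |
| Change in study treatment | Met, through the hold in 5.1.4.3 and 5.1.4.6 | Met only if the investigator chooses to interrupt or stop fulvestrant |
| Intervention or concomitant-therapy change | Not met | Not met |
| Clinically significant in the investigator's judgment | Not needed | Decides the matter if treatment is unchanged |

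**Step 2. See which tables are touched.** Adverse event tables in Section 6.5 inherit the difference. Laboratory tables by grade do not depend on adverse event reporting, and the schedule footnotes in Appendices 1 and 2 have creatinine monitored at each cycle in both arms.

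**Step 3. Size.** Let the true incidence p of Grade 2 or higher elevation be equal in the arms. Let a be the share reported in Arm A, and q the share of *all* Arm B elevations that go unreported. Then

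apparent ratio = a × p / ((1 - q) × p) = a / (1 - q).

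With a = 1:
- q = 0.10: 1/0.90 = 1.11
- q = 0.25: 1/0.75 = 1.33
- q = 0.50: 1/0.50 = 2.0

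Incomplete application of the hold shrinks the ratio. For example, a = 0.90 with q = 0.25 gives 0.90/0.75 = 1.20.

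If only a share s of elevations is asymptomatic, and a share u of those is unreported, then q = s × u. With s = 0.5 (assumed), u = 0.25, 0.50 and 0.75 give 1/0.875 = 1.14, 1/0.75 = 1.33 and 1/0.625 = 1.60.

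**Step 4. Absolute counts.** Section 6.1 plans about 152 patients at 1:1, so 152/2 = 76 per arm. Expected patients reported = 76 × p in Arm A and 76 × p × (1 - q) in Arm B; the spurious difference is p × q. The values of p and q are assumed.

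| p | Arm A | Arm B, q = 0.25 | Arm B, q = 0.50 | Spurious difference, percentage points (q = 0.25; 0.50) |
|---|---|---|---|---|
| 2% | 1.5 | 1.1 | 0.8 | 0.5; 1.0 |
| 5% | 3.8 | 2.9 | 1.9 | 1.25; 2.5 |
| 10% | 7.6 | 5.7 | 3.8 | 2.5; 5.0 |

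The only clinical renal rate in the documents is acute kidney injury in 2 of 148 GDC-0810 patients (Section 5.1.4.3), neither case considered related. It is a different measure from Grade 2 or higher creatinine, but at that rate 76 × 2/148 is about 1 patient.

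**The case against.** **The asymmetry is not absolute.** A reader might infer that every Grade 2 or higher rise is an adverse event in Arm A and that reporting is simply optional in Arm B. The documents support neither. The Arm A wording is that treatment should be held, and a rise found while drug is already interrupted or stopped changes no treatment. In Arm B, symptoms, an intervention, a concomitant-therapy change, or an interruption or discontinuation of fulvestrant all make reporting mandatory; the bar on modifying fulvestrant concerns dose level only. This stands and narrows the point to isolated, asymptomatic rises managed as written. It does not close the gap, because the shared triggers apply to both arms and the hold to one.

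**An unaffected summary already exists.** Section 6.5 tabulates all laboratory data by grade. This stands too: a reader might infer that the whole renal safety comparison is distorted, but only the adverse event tables are. What is missing is a statement of which table to rely on.

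**Little turns on it now.** Section 6.1 calls the trial hypothesis-generating, enrollment and development have stopped, counts are likely small, and Section 6.5 specifies no between-arm test of adverse events. The tilt also runs against GDC-0810, so it would not by itself hide a renal signal for that drug. This limits the importance. It does not remove the point, since the stated safety objective compares adverse event frequency and the direction of the tilt is predictable.

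**A tempting remedy goes too far.** A reader might conclude that creatinine adverse events already recorded should be left out of the comparison. The study team is already unblinded (Sections 5.1 and 5.1.2), so dropping a planned comparison at this stage, in the experimental drug's favour, would create a worse problem than the one it solves.

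**Conclusion.** The point holds in a limited form. For isolated, asymptomatic Grade 2 or higher creatinine rises managed as the protocol directs, adverse event ascertainment differs by arm. Creatinine adverse event counts, including those leading to interruption, tilt against GDC-0810; the graded laboratory tables are unaffected.

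The size cannot be estimated from the documents. An apparent ratio of 1.11 to 2.0 for q from 0.10 to 0.50 rests on equal true incidence, complete reporting in Arm A and an assumed q defined over all Arm B elevations. Much larger ratios can be produced (q = 0.75 gives 1/0.25 = 4.0), but that requires three quarters of all Arm B elevations, symptomatic ones included, to go unreported, and nothing in the documents supports it. Absolute differences are likely a few patients at most, fewer still because enrollment stopped and the number enrolled is not stated.

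**What to change.** **Section 6.5, two sentences.** State that the between-arm comparison of creatinine elevation is based on the worst treatment-emergent CTCAE grade from laboratory data, by arm. State that the creatinine adverse event table is shown alongside it, with a note that the reporting trigger differs by arm. Keep all adverse event data already collected.

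**Section 5.3.5.4, optional, for patients still on treatment.** Add that any treatment-emergent Grade 2 or higher creatinine elevation is recorded as an adverse event in both arms, whether or not study treatment changes.

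**Cost.** The Section 6.5 change needs no new test or data, because creatinine is already monitored each cycle in both arms. The optional criterion means a few more Arm B adverse event entries, an amendment with the approvals described in Section 9.6, and two ascertainment periods to footnote. Neither change alters any hold or restart rule.
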